### Weeks 3-8 – weekly phone calls

Good morning/afternoon I am \_\_\_\_\_ from the University of Michigan Mott Children's hospital. The purpose of this call is to follow up with you regarding you or your child's experience with the ssNPA over the past week.

Did you fill out the weekly survey for this week?

*\*If yes\* [skip to the bottom to the adverse events evaluation]*

*\*If no\** Alright, well then I have a few questions to ask you.

Did you have any difficulty with using the ssNPA over this past week? *\*If answers yes\** Could you describe those difficulties to me?

On average, how long did your child use the ssNPA each night/day?

How has your child been tolerating the device?

Did you have to re-insert or re-adjust the device during the night? If so, on average how many times did you have to get up to do this?

What was the level of perceived comfort of your child as they wore the device during the night or, if applicable, during the day.

Did the frequency and/or amplitude of your child's snores change over the week?

Did you notice any apneas during the night?

How has your child been sleeping overall?

Does your child seem more rested during the day?

Did you have any difficulties or adverse events with the device? Did you notice any nosebleeds, irritation, or any of the adverse events listed on your instruction form during your child's use of the device?

Any other comments or concerns about usage that you would like to bring up?

Thank you very much for your time. I will follow up with you again next week.

## Appendix I

Subject ID

--	--	--	--

Today's date: \_\_\_\_\_

### ssNPA User Feedback Questionnaire - DAY ONE

Thank you for participating in the ssNPA sleep study. Please let us know about you and your child's experience last night/yesterday using the ssNPA device by circling responses below:

1. Device insertion was....

- 1 - Extremely difficult
- 2 - Difficult
- 3 - Neutral
- 4 - Easy
- 5 - Extremely easy

2. Once placed, the device was...

- 1 - Not tolerated
- 2 - Poorly tolerated
- 3 - Neutral
- 4 - Tolerated
- 5 - Well-tolerated

3. During the night, the device came out completely and needed to be re-inserted...

- 1 - Very frequently
- 2 - Frequently
- 3 - Sometimes
- 4 - Rarely
- 5 - Not at all

4. During the night, the device came out partially and needed to be adjusted...

- 1 - Very frequently
- 2 - Frequently
- 3 - Sometimes
- 4 - Rarely
- 5 - Not at all

5. On a typical night, how many times do you usually get up in the middle of the night to check on/adjust your sleeping child and/or their sleep apnea device: \_\_

6. With the ssNPA, how many times did you have to get up during the night to optimize position of the device: \_\_

7. Please rate the level perceived comfort of your child wearing the device during the night...

- 1 – Very uncomfortable
- 2 – Uncomfortable
- 3 – Neutral
- 4 – Comfortable
- 5 – Very comfortable

8. If applicable, please rate the perceived comfort of the device during the day...

- 1 – Very comfortable
- 2 – Uncomfortable
- 3 – Neutral
- 4 – Comfortable
- 5 – Very comfortable

9. While using the device, my child's sleep was

- 1 – Much less restful
- 2 – Less restful
- 3 – Stable
- 4 – More restful
- 5 – Much more restful

10. While using the device, my child's snoring occurred

- 1 – Much less often
- 2 – Less often
- 3 – Unchanged
- 4 – More often
- 5 – Much more

11. While using the device, my child's snores were...

- 1 – Much louder
- 2 – Louder
- 3 – Unchanged
- 4 – Quieter
- 5 – Much quieter

12. In the morning, my child appeared...

- 1 – Much more tired
- 2 – More tired
- 3 – Unchanged
- 4 – Less tired
- 5 – Much less tired

Do you have any other comments or suggestions that you would like to share regarding your experience using the ssNPA?

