## **9.2 Study Assessments**

### **Stage 1: Initial clinical assessment**

After consent (and assent where appropriate) has been obtained, the PI or an otolaryngologist on the team, will perform an endoscopic measurement of the patient's airway to select the correct ssNPA length to bypass obstruction (a series of ssNPAs with pre-made lengths will be available). The ssNPA will be fully inserted through the nose by the Otolaryngologist and endoscopically checked to ensure adequate length bypassing obstruction and proper fit within the nose (see Appendix D for device sizing). Initial placement may be performed following topical nasal lidocaine/neosynephrine, which is commonly performed in routine flexible awake laryngoscopy. In our usability testing with patients and team members, brief mild discomfort can occur during initial placement, which resolves in seconds once the ssNPA is in place. In our observations, the brief initial discomfort improves with increased use, with acclimation of nasal environment.

Caregivers will be trained to perform the ssNPA insertion on the child in the clinic. In addition, they will be given an Instruction Brochure which provides information about OSA, demonstrates how to use the ssNPA, and provides information on the safety concerns of and proper care for the ssNPA device. The materials have been developed in concert with our tracheostomy team and are based on materials that provides similar robust care education. Families will be provided with a copy of the ssNPA desensitization protocol for the next 8-week (or less) desensitization home evaluation (see Appendices E-G for the caregiver documentation). We also will provide extra ssNPA devices to the patient so the device can be replaced bi-weekly.

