### **Stage 2: 8-week home evaluation**

After the first clinical assessment, the subject will be sent home with the ssNPA in place for home evaluation purposes for approximately 8 weeks, with two clinical in-person check-ins at weeks 2 and 4. As HUAO often results in obstructive events, both at night and while awake, we anticipate the ssNPA may be used for a large proportion of a 24-hour period in many children. The ssNPA desensitization protocol provides step-by-step instructions on how to help children get comfortable with placement of the device during daytime, after which, they will progress to use the ssNPA at night. Our team will work closely with parents/caregivers to follow instructions in the protocol to achieve adherence to ssNPA during these 8 weeks. The parent or guardian will be instructed how to insert the ssNPA and will be encouraged to have the child wear it for increasing intervals while awake to allow the child to acclimate to wearing it. This will also prepare them for wearing the device during the night. If the child feels comfortable with the ssNPA, it will be kept in place during the day as well. Feedback from families regarding desensitization during the R61 phase will optimize the desensitization protocol for the R33 phase.

Demonstration and instruction will be provided on cleaning and suctioning (Appendix F); the latter is required for any build-up of nasal secretion, particularly during respiratory illness. Indeed, during periods of respiratory illness, the ssNPA may provide relief for breathing disturbances, as has been observed in our pilot patients. Adherence will be followed and fostered by a registered nurse with extensive experience in desensitization among children in the Pediatric Sleep Clinic who require PAP. Customized ssNPA desensitization will be modeled on our experience with PAP desensitization. These efforts to promote adherence will match or exceed what we routinely provide to achieve a PAP adherence rate of 60-70% in children.

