Families will return to the clinic at weeks 2 and 4 to ensure optimal care and evaluate the device safety, tolerability, and acceptability. In between the clinic visits, regular contact will be made with families by the team, daily during the first week and weekly by the 2nd week (see Appendices H-K). During these calls, caregivers will report night to night witnessed apneas, improvement in daytime awareness, improvement in sleeping patterns of the patient, and any adverse events. Beside the two clinical visits at 2nd and 4th week, the number and frequency of extra visits will depend on: (1) the child's current threshold; and (2) how the child and family advance through each step of the desensitization protocol. The decision to hold on a particular step of the desensitization program will be based on whether the child's current level of anxiety or opposition is elevated. A recommendation to discontinue ssNPA treatment may be made if the child or family do not make progress with wearing the device in 2-4 weeks (depending on the number of visits during that time). Discontinuation of ssNPA therapy may occur after case consultation with other members of the study team to ensure that all strategies have been considered.

Evaluation of the device safety, tolerability, and acceptability will be assessed by a survey of patients and caregivers using a validated questionnaire with 10-point response scale (Appendix K). Mean and standard deviation scores as well as the percentage of those reporting satisfactory or better will be assessed. Device safety will be determined by adverse events

Table 3. Milestones for successful completion of the R61 phase

R61 Milestones	Goal (out of 5 subjects)
1. Device optimization and manufacturing in clean/sterile manner	100%
2. Parent report of ease of insertion; $\geq 5$ on Likert scale of 1-10	60% (3 of 5)
3. Child able to tolerate device in place	60% (3 of 5)
4. Child able to maintain device in place during sleep	60% (3 of 5)
5. Parent report of adherence based on diary	60% (3 of 5)
6. Comfort rating $\geq 6$ on Likert scale of 1-10	60% (3 of 5)

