### First two weeks – daily phone calls

#### **Baseline**

Good morning/afternoon I am \_\_\_\_\_ from the University of Michigan Mott Children's hospital. The purpose of this call is to follow up with you regarding you or your child's experience with the ssNPA last night.

Did you fill out the daily survey from last night?

*\*If yes\* [skip to the bottom to the adverse events evaluation]*

*\*If no\* Alright, well then I have a few questions to ask you.*

Did you have any difficulty with using the ssNPA last night? *\*If answers yes\* Could you describe those difficulties to me?*

How long did your child use the ssNPA last night?

How did your child tolerate the device?

Did you have to re-insert or re-adjust the device during the night? If so, how many times did you have to get up to do this?

What was the level of perceived comfort of your child as they wore the device during the night or, if applicable, during the day.

Did the frequency and/or amplitude of your child's snores change last night?

Did you notice any apneas during the night?

How did your child sleep overall?

Does your child seem more rested today?

Did you have any difficulties or adverse events with the device? Did you notice any nosebleeds, irritation, or any of the adverse events listed on your instruction form during your child's use of the device?

Tonight, you will insert the ssNPA device again for overnight use. Remember that if your child feels comfortable with the device in place in the morning, you can leave it in place during the daytime as well. Please fill out the daily survey and we will call you tomorrow to follow-up with you as well.

Do you have any other comments/concerns/questions?

Thank you for your time.

---

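### The Day-One, Daily and Weekly surveys cannot separate caregiver insertions from the clinic insertion or from periods with no insertion

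*Combined protocol and SAP*

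**What the plan says.** All three recurring surveys open with the same item, "Device insertion was", followed by five options. None stands for no insertion, and no item on the form asks who placed the device. The caregiver reports the experience of "using the ssNPA device by circling responses below". Another item on the same forms is conditional: "If applicable, please rate the perceived comfort of the device during the day".

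Section 9.2, Stage 1 describes the first placement: "The ssNPA will be fully inserted through the nose by the Otolaryngologist", possibly after a topical anaesthetic and decongestant. Caregivers are also trained in the clinic to insert the device on the child. Stage 2 then begins: "the subject will be sent home with the ssNPA in place for home evaluation purposes". The daily call script in Appendix H tells the caregiver to insert the device again that night, and adds that if the child is comfortable in the morning "you can leave it in place during the daytime as well". Section 2.2 calls for a daily check, with a change only when needed.

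Ease of use is part of the R61 primary objective (Section 4.1). Optimizing the insertion protocol and optimizing the surveys are R61 secondary objectives (Section 4.2), and Section 10.3.2 wants insertion to be acceptable to caregivers doing it themselves. Table 3 sets a milestone, "Parent report of ease of insertion", of at least 5 on a 1-10 scale in 60% (3 of 5) of subjects.

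**The concern.** What R61 needs to know about insertion is how a parent or other home caregiver finds it. Section 3.1 makes this the contrast with the nasal trumpet, which has to be placed by a health professional. A rating informs that question only if it refers to an insertion the caregiver performed.

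The forms do not secure this. A Day-One rating may describe a specialist's placement, possibly under topical anaesthetic. A later daily rating may cover a period in which the device simply stayed in. A caregiver with nothing to rate can circle the neutral option, repeat an old impression, circle an easy option, or leave the item blank, and a blank looks the same as an overlooked item. Whoever summarises the ratings could not tell these cases apart, and the evidence used to refine the insertion protocol for R33 would be harder to interpret.

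**Working it through.** The point concerns form wording, so the check is mainly a comparison of passages.

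**1. The plan's own figure.** The only stated number tied to ease of insertion is the milestone: 3/5 = 0.60, which reproduces the stated 60%. With five children, each child moves the result by 1/5 = 20 percentage points.

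**2. What the forms can record.** Item 1 is the same in Appendices I, J and K: five options, no opt-out, no inserter. The conditional wording on daytime comfort shows that the forms allow for an item that may not apply, but item 1 was not given that wording.

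**3. Can a form refer to something other than a caregiver insertion?**
- *Day One.* The otolaryngologist inserts the device and the child leaves wearing it. The caregiver may also have inserted it during clinic training or overnight. The form does not say which insertion is rated.
- *Daily.* The script expects an insertion each night but permits the device to stay in by day, and Stage 2 also allows this for a comfortable child. A form without a new insertion is therefore possible.
- *Weekly.* A week with no insertion is less likely, but the form could not show it.

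**4. Does another source recover the information?** Only in part. Item 3 asks how often the device came out and had to be re-inserted, so it signals some overnight re-insertions, but not whether or by whom the device was placed beforehand. In the call scripts, a completed survey sends the caller straight to the adverse-event questions. The fallback questions ask about re-insertion at night, not about who made the initial placement.

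**5. Which form feeds the milestone?** The milestone uses a 1-10 scale; item 1 in Appendices I to K runs 1-5. The only 1-10 insertion item shown is the overall rating in Appendix M, which looks back over about two months. Yet Section 9.2, Stage 2 describes Appendix K as a 10-point questionnaire for safety, tolerability and acceptability. The plan does not name the source form.

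**6. Illustration only.** Let m be the caregiver's true mean rating on 1-5, f the share of forms without a caregiver insertion, and a the answer circled on those forms. The recorded mean is (1 − f)·m + f·a. The documents give none of these three values.
- m = 2, a = 3: f = 0.25 gives 0.75×2 + 0.25×3 = 2.25; f = 0.50 gives 2.50.
- m = 4, a = 3: f = 0.25 gives 0.75×4 + 0.25×3 = 3.75; f = 0.50 gives 3.50.
- m = 2, a = 5: f = 0.50 gives 0.50×2 + 0.50×5 = 3.50.

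The recorded mean can move up or down. No estimate of bias follows. The plan also does not commit to averaging item 1 over daily forms: the means and standard deviations it specifies are for 10-point measures.

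**The case against.** The strongest reply is that the problem may be rare and may not touch anything decisive. The daily script expects a nightly insertion. Section 2.2 makes night use the rule and daytime use conditional. Desensitization by increasing periods of awake wear implies repeated insertion. Caregivers are trained to insert in the clinic, and the teaching record lists insertion as a skill to complete, so even a Day-One rating may be the caregiver's own. R61 is a descriptive phase of five children, and its 1-10 milestone fits Appendix M. The instruction brochure and desensitization protocol, which may govern removal and re-insertion, are not in the text available for this review.

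Most of this stands, and it rules out several stronger readings that a reader might infer:
- *That every survey has the defect.* Appendix M asks for one overall rating and has no day-by-day problem.
- *That caregivers are forced to give a rating.* No text forbids leaving the item blank.
- *That insertion occurs only as often as replacement.* The bi-weekly interval in Stage 1 concerns swapping in a fresh device. It is not an insertion frequency.
- *That the ratings are biased toward easy, most of all in families that avoid re-insertion.* The documents say nothing about how caregivers would answer, and the illustration shows that the direction can reverse.

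What the reply does not remove is that the forms cannot identify a caregiver insertion. Clinic training makes the Day-One answer more ambiguous, since either insertion could be the one rated.

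**Conclusion.** The point holds as a limit on interpretation. As worded, item 1 of Appendices I, J and K can mix caregiver insertions, the clinic insertion and periods with no insertion, and the form gives no means of separating them. This rests only on the item wording and on the placement and wear instructions in Sections 2.2 and 9.2 and Appendix H.

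Its size cannot be stated, because neither the share of affected forms nor the answers given on them can be derived. A reader might infer that the R61 ease-of-insertion milestone is compromised. The documents do not support that: the milestone's scale matches Appendix M, and it would be exposed only if Appendix K, which Section 9.2 cites, is in fact its source. The change is worth making because it costs little, caregiver insertion is something R61 sets out to assess, and optimizing the surveys is itself an R61 objective.

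**What to change.** - Before item 1 in Appendices I, J and K add: 'Did you or another home caregiver insert the device in this period? If no, skip item 1.'
- Reword item 1 to: 'When you inserted the device, insertion was...'
- Summarise ease of insertion per child over caregiver insertions only, and report the number of rated forms for each child.
- State which form and item feed the ease-of-insertion milestone in Table 3 and Section 10.3.1, and reconcile the description of Appendix K as a 10-point instrument with its five-point items. If Appendix M is the source, check the direction of its scale as a separate matter: there 1 is the easy end and 10 the difficult end, so a threshold of at least 5 would count harder insertions as success.

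The cost is one yes/no line and a short rewording on three forms, plus a sentence in the analysis section. The downside is fewer insertion ratings per child, though each one would refer to a caregiver's insertion.

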### **4.2 Secondary Objectives R61 phase**

1. Confirm ssNPA device design
2. Evaluate changes in sleep quality, snoring, and daytime sleepiness
3. Optimize the ssNPA insertion protocol
4. Optimize the ssNPA sizing protocol
5. Optimize the surveys/questionnaires for use in the larger clinical study

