### ssNPA User Feedback Questionnaire - DAILY

Thank you for participating in the ssNPA sleep study. Please let us know about you and your child's experience last night/yesterday using the ssNPA device by circling responses below:

1. Device insertion was....

- 1 - Extremely difficult
- 2 - Difficult
- 3 - Neutral
- 4 - Easy
- 5 - Extremely easy

2. Once placed, the device was...

- 1 – Not tolerated
- 2 – Poorly tolerated
- 3 - Neutral
- 4 – Tolerated
- 5 – Well-tolerated

3. During the night, the device came out completely and needed to be re-inserted...

- 1 – Very frequently
- 2 – Frequently
- 3 – Sometimes
- 4 – Rarely
- 5 – Not at all

4. During the night, the device came out partially and needed to be adjusted...

- 1 – Very frequently
- 2 – Frequently
- 3 – Sometimes
- 4 – Rarely
- 5 – Not at all

5. With the ssNPA, how many times did you have to get up during the night to optimize position of the device: \_\_\_\_\_

6. Please rate the level perceived comfort of your child wearing the device during the night...

- 1 – Very uncomfortable
- 2 – Uncomfortable
- 3 – Neutral
- 4 – Comfortable
- 5 – Very comfortable

7. If applicable, please rate the perceived comfort of the device during the day...

- 1 – Very uncomfortable
- 2 – Uncomfortable
- 3 – Neutral
- 4 – Comfortable
- 5 – Very comfortable

8. While using the device, my child's sleep was...

- 1 – Much less restful
- 2 – Less restful
- 3 - Stable
- 4 – More restful
- 5- Much more restful

9. While using the device, my child's snoring occurred...

- 1 – Much less often
- 2 – Less often
- 3 – Unchanged
- 4 – More often
- 5 – Much more

10. While using the device, my child's snores were...

- 1 – Much louder
- 2 – Louder
- 3 – Unchanged
- 4 – Quieter
- 5 – Much quieter

11. In the morning, my child appeared...

- 1 – Much more tired
- 2 – More tired
- 3 – Unchanged
- 4 – Less tired
- 5- Much less tired

Do you have any other comments or suggestions that you would like to share regarding your experience using the ssNPA?

---

\_\_\_\_\_

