### ssNPA User Feedback Questionnaire - WEEKLY

Thank you for participating in the ssNPA sleep study. Please let us know about you and your child's experience OVER THE PAST WEEK using the ssNPA device by circling responses below:

1. Device insertion was....

- 1 - Extremely difficult
- 2 - Difficult
- 3 - Neutral
- 4 - Easy
- 5 - Extremely easy

2. Once placed, the device was...

- 1 - Not tolerated
- 2 - Poorly tolerated
- 3 - Neutral
- 4 - Tolerated
- 5 - Well-tolerated

3. During the night, the device came out completely and needed to be re-inserted...

- 1 - Very frequently
- 2 - Frequently
- 3 - Sometimes
- 4 - Rarely
- 5 - Not at all

4. During the night, the device came out partially and needed to be adjusted...

- 1 - Very frequently
- 2 - Frequently
- 3 - Sometimes
- 4 - Rarely
- 5 - Not at all

5. With the ssNPA, how many times did you have to get up on average during the night to optimize position of the device: \_\_\_\_\_

6. Please rate the level perceived comfort of your child wearing the device during the night...

- 1 – Very uncomfortable
- 2 – Uncomfortable
- 3 – Neutral
- 4 – Comfortable
- 5 – Very comfortable

7. If applicable, please rate the perceived comfort of the device during the day...

- 1 – Very uncomfortable
- 2 – Uncomfortable
- 3 – Neutral
- 4 – Comfortable
- 5 – Very comfortable

8. While using the device, my child's sleep was

- 1 – Much less restful
- 2 – Less restful
- 3 – Stable
- 4 – More restful
- 5 – Much more restful

9. While using the device, my child's snoring occurred...

- 1 – Much less often
- 2 – Less often
- 3 – Unchanged
- 4 – More often
- 5 – Much more

10. While using the device, my child's snores were...

- 1 – Much louder
- 2 – Louder
- 3 – Unchanged
- 4 – Quieter
- 5 – Much quieter

11. In the morning, my child appeared...

- 1 – Much more tired
- 2 – More tired
- 3 – Unchanged
- 4 – Less tired
- 5 – Much less tired

Do you have any other comments or suggestions that you would like to share regarding your experience using the ssNPA?

4 of 4

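### The Day-One survey's daytime-comfort item gives codes 1 and 5 the same best label and has no worst option, so an answer of 1 cannot be interpreted (minor form error)

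*Combined protocol and SAP*

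**What the plan says.** Appendix I, item 8, reads "8. If applicable, please rate the perceived comfort of the device during the day". Its five options are "1 – Very comfortable", then uncomfortable at 2, neutral at 3, comfortable at 4, and "5 – Very comfortable". The daytime item in Appendix J (item 7) is otherwise the same but begins at "1 – Very uncomfortable", as does item 7 in Appendix K. Item 7 of Appendix I, on night comfort, also begins at the very uncomfortable end.

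Section 4.1 includes comfort in the R61 primary objective. Section 5.1 says that safety and tolerability outcomes, comfort among them, are measured with 10-point and Likert scales, and Section 9.2 (Stage 2) says that comfort level is assessed by Likert scoring. The R61 milestones in Table 3 and Section 10.3.1 set the comfort criterion on a 1-10 scale. Section 4.2 also makes it an R61 objective to optimise the surveys for the larger study.

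**The concern.** Item 8 collects data, so a wrong label changes what the stored value means. A caregiver who reads the labels can report the best experience by circling either 1 or 5. A caregiver who follows the pattern of item 7 will circle 1 for the worst. A caregiver of a very uncomfortable child who reads the labels finds no matching answer and may settle for 2. Once only the number is stored, the meanings behind a 1 cannot be separated.

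What is at stake is the Day-One daytime-comfort data, and the form's fitness for use in the larger study if it is carried forward unchanged.

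**Working it through.** The plan gives no figure for this item, so there is nothing to reproduce. The check sets the forms side by side and then bounds the effect.

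**1. Bottom label of each comfort item**

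- Appendix I item 7 (night): very uncomfortable
- Appendix I item 8 (day): very comfortable
- Appendix J items 6 and 7 (night, day): very uncomfortable
- Appendix K items 6 and 7 (night, day): very uncomfortable

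Five of the six comfort items agree and one differs. In the odd one, code 2 is still uncomfortable and code 5 is still very comfortable. The scale as a whole was therefore not reversed; only the label at code 1 is wrong.

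**2. Direction of all verbally anchored 1-5 items**

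- Appendix I has 10 such items. Eight have 5 as the favourable end (items 1, 2, 3, 4, 7, 9, 11, 12), one is ambiguous (item 8) and one runs the other way (item 10, snoring frequency).
- Appendices J and K have 10 each. Nine have 5 as the favourable end and one runs the other way (item 9, snoring frequency).

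With the item 8 label corrected, Appendix I would have 9 of 10, the same as the other two forms.

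**3. Size of the ambiguity**

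An answer of 1 may stand for a true 1 or a true 5, so the ambiguity is 5 - 1 = 4 points. If k of n respondents circle 1, the mean of item 8 read one way differs from the mean read the other way by 4k/n. With one such answer among the 5 planned R61 children, that is 4 × 1/5 = 0.8 points. Item 8 is answered only if applicable, so n may be smaller. With three respondents (an assumption) it is 4 × 1/3 = 1.33 points. These figures are illustrations, because no analysis in the plan takes a mean of this item.

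**4. Whether another step would catch it**

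The call script for the first two weeks (Appendix H) asks about comfort only when the survey was not filled in. When it was filled in, the caller goes straight to the adverse-event questions. A completed form with an ambiguous 1 is therefore not checked by the script as written.

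**5. Whether a decision rule uses the item**

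The R61 comfort criterion is on a 1-10 scale. That matches item 2 of Appendix M, which runs correctly from extremely uncomfortable to extremely comfortable. The R33 primary outcome is AHI response at Week 8. Neither uses Appendix I item 8.

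**The case against.** The strongest case on the other side is that this is a one-word slip of little consequence. The item covers a single day, is optional and feeds no stated milestone or test. The same form records tolerability (item 2) and night comfort (item 7) with correct labels and has a free-text box, and the call script asks about difficulties and adverse events. Most caregivers, seeing uncomfortable at 2 and the pattern of item 7, might take 1 as the worst. All of this stands as a limit on impact. It does not make an answer of 1 interpretable, and guessing from position is not a scoring rule.

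A reader might go further and infer that the snoring-frequency item is also faulty. On Appendices I, J and K it starts at "1 – Much less often", so a high code means worse snoring, while the next item, on loudness, ends at "5 – Much quieter". Section 4.2 lists as an objective: "Evaluate changes in sleep quality, snoring, and daytime sleepiness". The documents do not support calling this an error. The labels are ordered and unambiguous, no score pools the items, and the paired tests in Section 10.3.2 are specified for sleep quality and daytime sleepiness, not snoring. If the two snoring items were averaged without reversal, the best answers to both would give (1 + 5)/2 = 3, which reads as unchanged. Nothing in the plan says they will be averaged.

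A reader might also infer from Section 9.2 that worse snoring would be counted as a satisfactory result, because that section says "Mean and standard deviation scores as well as the percentage of those reporting satisfactory or better will be assessed". That sentence concerns a 10-point questionnaire on safety, tolerability and acceptability. The section cites Appendix K for it, but Appendix K is printed with 1-5 items. Section 9.2 (Stage 3) plans the same summary for Appendix M, which is 10-point and has no snoring item. Counting a high snoring code as satisfactory would also need a cut-off that the plan does not give.

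**Conclusion.** Appendix I item 8 is wrong as written, and the error is minor. An answer of 1 cannot be interpreted, with an ambiguity of 4 points on the 5-point scale. The effect on any summary depends on how many caregivers circle 1 and how many answer the item, and the documents give neither.

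Comfort is part of the R61 primary objective, so a reader might infer that the R61 go-forward decision is compromised. It is not: the comfort milestone is on a 1-10 scale with a correctly anchored matching item, and the R33 AHI outcome is unaffected. The conclusion assumes that the form given to families carries the label printed in Appendix I. The five sibling items, all printed correctly, make a text-extraction fault unlikely.

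The snoring-frequency item is reverse-keyed but correctly labelled, and is not an error.

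**What to change.** Change option 1 of Appendix I item 8 to very uncomfortable, as in item 7 of the same form and in Appendices J and K.

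For forms already completed, flag each answer of 1 as ambiguous and ask the caregiver what was meant where that is still possible. The current call script would need an added prompt for this. Report Day-One daytime comfort twice, with code 1 read as the worst and as the best answer. Do not set those answers to missing: judged by position on the scale they may come from the least comfortable children, and dropping them could make comfort look better than it was.

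For snoring frequency, leave the forms as they are. Reordering an item already in use would create two versions with opposite codes. If the item is ever combined with others, add one line to the analysis plan saying that it is scored as 6 minus the code.

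The cost is a one-word form correction with a minor IRB amendment, a short call prompt, and one extra line in a descriptive table. Sample size, endpoints and visits do not change.
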